6.3. Secondary Efficacy Endpoints and Analysis

6.3.1. Key Secondary Efficacy Endpoints

The key secondary endpoints are the following:

1. change from baseline to week 15 in centrally read MD-CRS part I total score (TEV-50717 versus placebo)
2. CaGI-I at week 15 (TEV-50717 versus placebo)
3. CGI-I at week 15 (TEV-50717 versus placebo)
4. change from baseline to week 15 in centrally read UHDRS-TMC (TEV-50717 versus placebo)
5. change from baseline to week 15 in centrally read UHDRS-TMD (TEV-50717 versus placebo)

For a detailed description of scales, refer to the Section 6.2 of the study protocol.

6.3.1.1. Key Secondary Efficacy Endpoints Analysis

Analyses of the key secondary endpoints will be performed in a hierarchical manner as follows:

1. MD-CRS part I total score change from baseline to week 15 will be analyzed using a MMRM in the same fashion as the primary analysis, with the exception that the baseline value of MD-CRS part I total score will be included as the covariate instead of MD-CRS part II total score.

2. CaGI-I at week 15 will be analyzed using an MMRM model in the same fashion as the primary analysis, with the exceptions that the baseline value of CGI-S will be included as the covariate instead of MD-CRS part II total score and that the week variable will include 5 levels (weeks 3, 7, 9, 12, and 15).
3. CGI-I at week 15 will be analyzed using an MMRM model in the same fashion as the primary analysis, with the exceptions that the baseline value of CGI-S will be included as the covariate instead of MD-CRS part II total score and that the week variable will include 5 levels (weeks 3, 7, 9, 12, and 15).
4. UHDRS-TMC (centrally-read) change from baseline to week 15 will be analyzed using an MMRM model in the same fashion as the primary analysis, with the exception that the baseline value of UHDRS-TMC (centrally-read) will be included as the covariate instead of MD-CRS part II total score.
5. UHDRS-TMD (centrally-read) change from baseline to week 15 will be analyzed using an MMRM model in the same fashion as the primary analysis, with the exception that the baseline value of UHDRS-TMD (centrally-read) will be included as the covariate instead of MD-CRS part II total score.

For CaGI-I and CGI-I, in [Appendix 1](#), Step 1 should begin with week 3, week 7 and only then continue to week 9.

See Section [6.5.3](#) for definition of UHDRS-TMC and TMD, and Section [7](#) for description of multiplicity control of the key secondary endpoints.

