3.2. Modified Intent-to-Treat Analysis Set

The modified intent-to-treat (mITT) analysis set is a subset of the ITT analysis set including all randomized patients with at least 1 post-baseline centrally read MD-CRS part II assessment.

In the mITT analysis set, treatment will be assigned based on the treatment to which patients were randomized, regardless of which treatment they actually received.

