4.4. Study Days and Visits

Study days will be numbered relative to the baseline visit date. Day 1 is defined as the date of the baseline visit, and the first dose of the IMP will be taken the next morning (day 2). Days will be numbered relative to baseline (ie, ..., -2, -1, 1, 2, ...; day -1 being the day before the baseline visit).

For efficacy and safety by-visit analyses, data collected at post-baseline scheduled visits will be included using their scheduled visit.

Data collected at early termination and unscheduled visits will be included and assigned to a visit window as described below.

Table 2: Visit Windows for Early Termination Visit for Efficacy Assessments

Assessment ^a	Study Day Window	Scheduled Day	Scheduled Visit/Week
MD-CRS	Day 2 - 73	Day 63	Week 9
	Day 74 - 94	Day 84	Week 12
	Day 95 - EOT	Day 105	Week 15
	≥Day after EOT	Day 112	Week 16
CaGI-I, CGI-S, PGI-I	Day 2 - 35	Day 21	Week 3
	Day 36 - 53	Day 49	Week 7
	Day 54 - 73	Day 63	Week 9
	Day 74 - 94	Day 84	Week 12
	Day 95 - EOT	Day 105	Week 15
	≥Day after EOT	Day 112	Week 16
CGI-I	Day 2 - 10	Day 7	Week 1
	Day 11 - 17	Day 14	Week 2
	Day 18 – 24	Day 21	Week 3
	Day 25 - 31	Day 28	Week 4
	Day 32 - 38	Day 35	Week 5
	Day 39 - 45	Day 42	Week 6
	Day 46 - 53	Day 49	Week 7
	Day 54 - 73	Day 63	Week 9
	Day 74 - 94	Day 84	Week 12
	Day 95 - EOT	Day 105	Week 15
	≥Day after EOT	Day 112	Week 16
PEDI-CAT, PedsQL	Day 2 – EOT	Day 105	Week 15

Assessment ^a	Study Day Window	Scheduled Day	Scheduled Visit/Week
UHDRS-TMS, UHDRS-TMC, UHDRS-TMD	Day 2 - 73	Day 63	Week 9
	Day 74 - 94	Day 84	Week 12
	≥Day 95 - EOT	Day 105	Week 15

^a CaGI-I=Caregiver Global Impression of Improvement; CGI-I=Clinical Global Impression of Improvement; CGI-S=Clinical Global Impression of Severity; PGI-I=Patient Global Impression of Improvement; UHDRS-TMS=Unified Huntington’s Disease Rating Scale-Total Motor Score; UHDRS-TMC=Unified Huntington’s Disease Rating Scale-Total Maximal Chorea; UHDRS-TMD=Unified Huntington’s Disease Rating Scale-Total Maximal Dystonia; EOT=end of treatment

Table 3: Visit Windows for Early Termination Visit for Safety Assessments

Assessment ^a	Study Day Window	Scheduled day	Scheduled Visit/Week
Vital signs, Weight, C-SSRS, ESRS, CBCL- Syndrome Scale, ESS	Day 2 - 35	Day 21	Week 3
	Day 36 - 53	Day 49	Week 7
	Day 54 - 74	Day 63	Week 9
	Day 75 - 94	Day 84	Week 12
	Day 95 – EOT	Day 105	Week 15
	≥Day after EOT	Day 112	Week 16
ECG	Day 2 - 35	Day 21	Week 3
	Day 36 - 67	Day 49	Week 7
	Day 68 – EOT	Day 105	Week 15

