	≥Day after EOT	Day 112	Week 16
Laboratory tests other than pregnancy and drug screen	Day 2 – EOT	Day 105	Week 15
	≥Day after EOT	Day 112	Week 16
Orthostatic blood pressure, Physical exam, Neurological exam, height, CBCL-full assessment	Day 2 – EOT	Day 105	Week 15

^a CBCL=Child Behavior Checklist (for ages 6-18); C-SSRS=Columbia-Suicide Severity Rating Scale; ECG=electrocardiogram; ESRS=Extrapyramidal Symptom Rating Scale (subscales I and II); ESS =Epworth Sleepiness Scale (for children and adolescents); EOT=end of treatment

After mapping the data to the analysis visits of unscheduled and early termination visits, the following rules will apply unless other handling is specified for a particular analysis:

- If there is a scheduled visit in the analysis window, the last non- missing scheduled visit will be selected.
- If there is no scheduled visit, but early termination visit, early termination visit will be selected.

- If there are no scheduled or early termination visits, the record closest to the planned assessment day will be selected for analysis.
- If there are no scheduled or early termination visits, and 2 records are equidistant from the scheduled day, then the later record will be selected.
- If a patient has no scheduled record or early termination/unscheduled visits in an analysis window, the patient will be considered missing at that visit.

For these analyses performed by time period, eg, adverse events, the following definitions will be used:

- Titration Period - from the first dose of treatment until the day of the week 7 visit. For patients discontinued before the week 7, the Titration Period is until the later of the last dose of treatment and the early termination visit.
- Maintenance Period - from the day after the week 7 visit until the day of the week 15 visit. If a patient enters the Maintenance Period but discontinues treatment early, the Maintenance Period is until the later of the last dose of treatment and the early termination visit.
- Overall Treatment Period - includes the Titration and the Maintenance Periods, if applicable.
- Follow-up Period - from the end of the Overall Treatment Period through the end of the study.

For last assessment, the last available non-missing value will be used. Unscheduled visits that could not be mapped will not be displayed in the safety by-visit summaries, but they will be considered for the endpoint/last assessment visit.

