6.3.1.2. Key Secondary Efficacy Endpoints Sensitivity Analysis

Sensitivity analyses for the key secondary endpoints will be performed in the same fashion as the primary endpoint. See Section [6.2.4](#) for details.

Some specific notes:

- The corresponding baseline or post-baseline assessment will be used for each secondary endpoint.
- Tipping point (MNAR) – For CaGI-I and CGI-I, the imputation model will include age group at baseline, region, treatment group, and CGI-S core at baseline, as well as the CaGI-I or CGI-I score at week 3, 7, 9 and week 12. MAR multiple imputation will be analyzed in a similar fashion with the same covariates.
- ANCOVA models will be fitted for change from baseline in MD-CRS part I total score to weeks 9, 12 and 15, and CaGI-I and CGI-I scores at weeks 3, 7, 9, 12 and 15.

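### On 37 of 52 titration window days, an early-termination CGI-I rating is mapped to a week that the key secondary CGI-I model and its imputation leave out

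*SAP*

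**What the plan says.** **Model weeks.** Section 6.3.1.1 analyses CaGI-I and CGI-I by MMRM and says of each that "the week variable will include 5 levels (weeks 3, 7, 9, 12, and 15". For the imputation of both scales it adds that "Step 1 should begin with week 3, week 7 and only then continue to week 9". Section 6.3.1.2 builds the tipping-point and MAR imputation models from baseline variables "as well as the CaGI-I or CGI-I score at week 3, 7, 9 and week 12". CGI-I at weeks 1, 2, 4, 5 and 6 appears in none of these.

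**Visit mapping.** Section 4.4 says: "Data collected at early termination and unscheduled visits will be included and assigned to a visit window as described below". In Table 2 the row group "CaGI-I, CGI-S, PGI-I" has two titration windows: days 2-35 (week 3) and days 36-53 (week 7). CGI-I has seven, one for each of weeks 1 to 7.

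**Selection.** Within a window the rule is: "If there is a scheduled visit in the analysis window, the last non- missing scheduled visit will be selected". If a window holds no record, "the patient will be considered missing at that visit". Section 4.4 leaves room for different handling in a particular analysis, but none is given for CGI-I.

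**Who is analysed.** The mITT set consists of "all randomized patients with at least 1 post-baseline centrally read MD-CRS part II assessment". Table 2 maps an ET MD-CRS on days 2-73 to week 9, so a patient who leaves during titration can be in mITT.

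**The concern.** The weekly CGI-I windows suit by-visit tables, but Section 6.3.1.1 gives the model no mapping of its own. An ET rating that Section 4.4 says will be included is therefore assigned to a week that the model and its imputation ignore.

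CGI-I is the only key secondary endpoint with this mismatch. For MD-CRS part I and the two UHDRS scores, the on-treatment windows and the model weeks are both 9, 12 and 15. For CaGI-I both are 3, 7, 9, 12 and 15.

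Section 4.3 does not require patients who stop treatment to return at week 15, so the ET rating may be the last one they have. The secondary estimands (Section 1.2) apply whether or not treatment was stopped, which makes the patient's own late data worth keeping. CGI-I is third in the testing order of Section 7 and gates UHDRS-TMC and UHDRS-TMD.

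**Working it through.** The SAP states no figure here, so the check is a count of Table 2 window days against the model weeks 3, 7, 9, 12 and 15.

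| ET day | CGI-I week | Days | In CGI-I model? | CaGI-I week |
|---|---|---|---|---|
| 2-10 | 1 | 9 | no | 3 |
| 11-17 | 2 | 7 | no | 3 |
| 18-24 | 3 | 7 | yes | 3 |
| 25-31 | 4 | 7 | no | 3 |
| 32-38 | 5 | 7 | no | 3 to day 35, then 7 |
| 39-45 | 6 | 7 | no | 7 |
| 46-53 | 7 | 8 | yes | 7 |

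**Step 1: mapping alone.**
- Outside the model: 9 + 7 + 7 + 7 + 7 = 37 days. Inside: 7 + 8 = 15. Total 52.
- 37/52 = 71%. Counting only to the scheduled week 7 day (days 2-49): 37/48 = 77%.

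**Step 2: what the 37 days mean.**
- Days 2-17 (16 days): no CGI-I at any model week. The whole series is imputed from baseline variables.
- Days 25-45 (21 days): the scheduled week 3 rating, if obtained, stays. Weeks 7-15 are imputed without the ET rating.
- Example: a patient has an ET visit on day 40. The caregiver rating enters as week 7. The physician rating goes to week 6 and is unused, so week 7 onward is imputed with week 3 as the only post-baseline predictor.

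**Step 3: add the scheduled-visit priority rule.** Assume the week 3 visit was held on day 21 and, for ET after day 49, the week 7 visit on day 49.
- CaGI-I: the scheduled record displaces ET ratings on days 22-35 (14 days) and 50-53 (4 days), so 18 of 52 are unused.
- CGI-I as written: 37 + days 22-24 (3) + days 50-53 (4) = 44 of 52 unused.

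**Step 4: apply the CaGI-I windows to CGI-I.** Unused days fall from 44 to 18, so 26 are recovered: days 2-17 (16) and days 36-45 (10). Days 25-35 (11) remain displaced by the scheduled week 3 rating; 26 + 11 = 37.

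**Step 5: distance from the nominal week.** The largest shift is day 2 to day 21, which is 19 days. Others are smaller: day 35 to 21 is 14, and day 36 to 49 is 13.

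**Step 6: patients.** The SAP gives no titration dropout rate. As an illustration only, each 5% of 65 is 65 × 0.05 = 3.25 patients. If their ET days were spread evenly over days 2-53, 3.25 × 0.71 = 2.3 of them would have the CGI-I rating mapped outside the model.

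**The case against.** **The windows follow the schedules.** CGI-I is listed weekly in titration and CaGI-I only at weeks 3 and 7, so each ET rating goes to its nearest scheduled week. The model also leaves out the scheduled week 1, 2, 4, 5 and 6 CGI-I of every patient. This explains the layout. It does not settle the matter: a continuing patient has later ratings in the model, whereas for a titration dropout the omitted rating may be the last.

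**71% against 0%.** A reader might infer that CGI-I loses 71% of ET ratings and CaGI-I none. The SAP does not support that. The zero holds for mapping only; with a week 3 visit on day 21, CaGI-I also loses ET ratings on days 22-35. The 71% is a share of days, not of ratings or patients.

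**Bias at week 15.** A reader might infer a biased treatment contrast. The documents show neither direction nor size. Week 15 is imputed for these patients either way. TEV-50717 patients who leave for tolerability, treatment-related adverse events or lack of efficacy are classed as MNAR, subject to blinded review, and imputed from placebo. The ET rating would still condition that imputation, but only as a predictor.

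**Discarded from the trial.** This is also too strong. The rating still appears in the by-visit responder analysis (Section 6.5.8).

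**Meaning of EOT.** Table 2 sends assessments after EOT to week 16, and Section 2.1 places the ET visit after the last dose. If EOT means the patient's own last treatment day, ET ratings on both scales could go to week 16. The contrast with CaGI-I would then vanish, but the CGI-I rating would still be unused. This needs a clarifying sentence.

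**Conclusion.** The point holds in a limited form. As written, an ET CGI-I rating on days 2-17 or 25-45 is absent from the key secondary model, its imputation and its sensitivity analyses, and no exception is specified. What is lost is an intermediate observation and an imputation predictor for patients who leave in titration, not their week 15 value. For ET on days 2-17 and 36-45, the caregiver and physician endpoints then use different data from the same visit.

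The size is 37 of 52 titration window days, of which 26 are recoverable by using the CaGI-I windows. This assumes that EOT in Table 2 does not redirect ET visits to week 16; the 26 also assumes a week 3 visit held on day 21. Only dropouts with a post-baseline central MD-CRS part II reading are affected. Their number, and any effect on the CGI-I contrast, cannot be derived from the SAP. The change is worth making because the rating is already collected and the correction is small.

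**What to change.** 1. For the CGI-I MMRM, its imputation and its sensitivity analyses only, map ET CGI-I ratings with the CaGI-I windows: days 2-35 to week 3, days 36-53 to week 7, and later windows as now.
2. State that only the scheduled week 3 or week 7 visit takes priority over the ET rating. Scheduled week 1, 2, 4, 5 and 6 ratings do not. Without this, the rule that picks the last scheduled record in a window could select, for example, a week 1 rating over an ET rating on day 12.
3. Keep the weekly windows for by-visit CGI-I summaries.
4. State that the week 16 row for assessments after EOT does not override these windows for ET visits.
5. Settle the rule blinded before the interim analysis. Sections 2.5.1 and 10.1 bar later changes to the main analysis of the key secondary endpoints.

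The cost is a footnote to Table 2 and a separate analysis-visit derivation for this model; no new data are needed. The downside is that an ET rating up to 19 days from the nominal week is used, as Table 2 already accepts for CaGI-I. ET ratings on days 25-35 stay displaced by a held week 3 visit, as they do for CaGI-I.

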6.3.1.2. Key Secondary Efficacy Endpoints Sensitivity Analysis

Sensitivity analyses for the key secondary endpoints will be performed in the same fashion as the primary endpoint. See Section [6.2.4](#) for details.

Some specific notes:

- The corresponding baseline or post-baseline assessment will be used for each secondary endpoint.
- Tipping point (MNAR) – For CaGI-I and CGI-I, the imputation model will include age group at baseline, region, treatment group, and CGI-S core at baseline, as well as the CaGI-I or CGI-I score at week 3, 7, 9 and week 12. MAR multiple imputation will be analyzed in a similar fashion with the same covariates.
- ANCOVA models will be fitted for change from baseline in MD-CRS part I total score to weeks 9, 12 and 15, and CaGI-I and CGI-I scores at weeks 3, 7, 9, 12 and 15.

6.4. Subgroup Analyses

Analyses of the primary and key secondary endpoints by subgroup below will be conducted using the mITT population:

- Gender: male and female;
- Race Group: white, black or African American, and other;

- Baseline Age Group (6-<12 years, 12-18 years inclusive);
- CYP2D6 impairment status (Yes/No);
- US vs outside of US (non-US).

As the total sample size is approximately 65 patients, the sub-group analysis will include descriptive statistics by subgroup, and no statistical models will be fitted. The subgroup analyses will be performed provided the minimum size of the smaller subgroup is at least 5 patients. Otherwise, the main analysis will be repeated on the larger subgroup.

6.5. Other Efficacy Endpoints and Analysis

Other efficacy endpoints (change from baseline to week 15/proportion at week 15; TEV-50717 versus placebo) are the following:

- MD-CRS physician rated:
 - MD-CRS part I total score change from baseline to week 15
 - MD-CRS part II total score change from baseline to week 15
 - MD-CRS Global Index (calculated from MD CRS parts I and II total scores as assessed by physician)
- MD-CRS Global Index (calculated from MD-CRS parts I and II total scores, centrally read)
- UHDRS:
 - UHDRS-TMS (physician rated)
 - UHDRS-TMC (physician rated)
 - UHDRS-TMD (physician rated)
- PEDI CAT
- PedsQL
- PGI-I
- CGI-S
- Response Analysis
 - CaGI-I response, defined as patients who are described by the caregiver as “Much Improved” or “Very Much Improved” in the CaGI-I score
 - CGI-I response, defined as patients who are described as “Much Improved” or “Very Much Improved” in the CGI-I score
 - CGI-S response, defined as patients who have a reduction of ≥ 1 point in the CGI-S score
 - PGI-I response, defined as patients who are described as “Much Improved” or “Somewhat Improved” in the PGI-I score

The mITT analysis set will be used for the analysis.

6.5.1. MD-CRS Global Index (calculated from MD-CRS parts I and II total scores, centrally read)

6.5.1.1. Definition

The MD-CRS Global Index is a global measure of the MD-CRS that consolidates the information from parts I and II using the method of weighted means of the 2 normalized indexes obtained from each part. The minimum score is 0 and the maximum score is 1.

The standardized/normalized score for each item of MD-CRS parts I and II with value X is calculated using the formula

$$X_{st} = \frac{X - X_{min}}{X_{max} - X_{min}}$$

where X_{max} is the maximum value for the score, and X_{min} is the minimum value for the score, or 4 and 0 respectively.

The normalized index for the scale, MD-CRS parts I or II, Index I or II, is calculated as the mean value of X_{st} .

The MD-CRS Global Index is the weighted mean of the normalized indexes for centrally read MD-CRS parts I and II using the formula:

$$Global\ Index = \frac{n_I \times Index_I + n_{II} \times Index_{II}}{n_I + n_{II}}$$

where n_I and n_{II} are the numbers of items in MD-CRS parts I and II respectively.

6.5.1.2. Analysis

The MD-CRS Global Index change from baseline to week 15 data will be analyzed using MMRM. The MMRM model will include age group at baseline, week (3 levels: weeks 9, 12, and 15), region, corresponding baseline value and treatment as fixed effects. The SAS code is below:

```
proc mixed Method=REML;  
  class usubjid arm avisitn agegrp region;  
  model chg=arm | avisitn agegrp region base / ddfm=kr;  
  repeated avisitn / type=un subject=usubjid;  
  lsmeans arm*avisitn / diff cl;  
  ods output diffs=diff(where=(avisitn=_avisitn) lsmeans=lsm;  
Run;
```

The LS mean and SE for the treatment groups, the LS mean difference, 2-sided 95% confidence interval (CI), and 1-sided p-value for the comparison (TEV-50717 versus placebo) at Week 15 will be presented. The p-value will be considered to be a nominal p-value.

A descriptive summary will be provided for all assessments and change from baseline, including the follow-up period.

6.5.2. MD-CRS Physician Rated

6.5.2.1. Definition

The local, physician rated MD-CRS part I and MD-CRS part II are additional efficacy endpoints of the study. The physician rated MD-CRS part I and MD-CRS part II endpoints include:

- MD-CRS part I total score (general assessment, physician rated) change from baseline to week 15
- MD-CRS part II total score (general assessment, physician rated) change from baseline to week 15
- MD-CRS Global Index (calculated from MD CRS parts I and II total scores as assessed by physician) change from baseline to Week 15

The calculation as described in Section 6.5.1.1 will be performed for physician-rated MD-CRS assessments to yield the MD-CRS Global Index.

6.5.2.2. Analysis

The data will be analyzed using MMRM similarly to the description in Section 6.5.1.2.

6.5.3. Unified Huntington’s Disease Rating Scale

6.5.3.1. Definition

UHDRS-TMS:

The UHDRS-TMS (physician rated) comprises a broad assessment of features associated with HD. The TMS component of UHDRS comprises 31 assessments from the 15 items of the UHDRS. The TMS is calculated as the sum of the 31 motor assessments, each of which range between 0 to 4. The minimum score is 0 (absent) and the maximum score is 124 (worst).

The UHDRS-TMS is administered at baseline and weeks 9, 12, and 15/ET visits.

UHDRS-TMC:

The UHDRS-TMC is part of the UHDRS-TMS assessment and evaluates the severity of chorea in the face, mouth, trunk, and the 4 extremities. The minimum score is 0 (absent) and the maximum score is 28 (marked/prolonged).

UHDRS-TMD:

The UHDRS-TMD is part of the UHDRS-TMS assessment and assesses the severity of dystonia in the trunk and the 4 extremities. The minimum score is 0 (absent) and the maximum score is 20 (marked/prolonged).

If responses of up to 25% of items are missing in UHDRS-TMS, UHDRS-TMC, or UHDRS-TMD (“scale”), the missing responses will be replaced by the average of the remaining responses

within each of the scales. If 8 or more of the items are missing, the missing items will not be replaced and the scale will be set to missing.

The UHDRS-TMC and TMD are administered at baseline and at weeks 9, 12, and 15/ET visits.

